4.1.5 Blinding and procedures for unblinding

4.1.5.1 Blinding

Not applicable

4.1.5.2 Procedures for emergency unblinding

Not applicable.

4.1.6 Packaging, labelling, and re-supply

For details of packaging and the description of the label, refer to the ISF.

Trial drug packages will have unique medication numbers which will be used for tracking purposes only. The medication numbers will not be linked to randomisation numbers.

Afatinib will be supplied:

- As film-coated tablets with available dosage strengths of 20 mg, 30 mg, 40 mg and 50 mg in child resistant plastic bottles. Each bottle containing 30 tablets.
- As capsules and solvent for oral solution. Afatinib solution will be prepared at site: two 200mg capsules must be dissolved in the co-supplied bottle of 100mL of solvent resulting in a concentration of 4mg/mL. See details in reconstitution instruction provided in the ISF. Dosing and administration is planned to be performed by the parents/caregivers with a co-supplied oral syringe suitable for the intended volume. The syringe can be connected to the bottle via an adapter plug. See details in handling instruction (illustration of administration procedure) provided in the ISF (also to be provided to parents/caregivers). The oral solution is stored in child resistant solvent bottles.

4.1.7 Storage conditions

Trial medication, which will be provided by the sponsor and/or a CRO appointed by the sponsor, must be kept in a secure, limited access storage area under the storage conditions defined below until supplied/administered to patient. Temperature logs must be maintained to make certain that the drug supplies are stored at the correct temperature. In case temperature would be out of range, this has to be reported in the ISF and the sponsor be notified.

Afatinib tablets:

Afatinib must be stored in the original package in order to protect from light. Film-coated tablets are humidity-sensitive; therefore, bottles must be kept tightly closed to protect from moisture. Tablets must be stored according to label instructions.

Proprietary confidential information.

© 2017 Boehringer Ingelheim International GmbH or one or more of its affiliated companies. All rights reserved.

This document may not - in full or in part - be passed on, reproduced, published or otherwise used without prior written permission.

Afatinib capsules and solvent:

Afatinib capsules must be stored in the original container in order to protect from moisture.

Solvent for Oral Solution must be stored according to label instructions.

After preparation, the solution is stable for 4 weeks at 25°C (date of preparing the oral solution has to be reported on the bottle label). The solution must be stored in the original solvent container/ amber glass bottle.

4.1.8 Drug accountability

Drug supplies, which will be provided by the sponsor or a CRO appointed by the sponsor, must be kept in a secure, limited access storage area under the storage conditions defined by the sponsor. Where necessary, a temperature log must be maintained to make certain that the drug supplies are stored at the correct temperature.

The investigator or delegate (e.g. pharmacist or study drug storage manager) will receive the investigational drugs delivered by the sponsor when the following requirements are fulfilled:

- approval of the study protocol by the IRB / ethics committee,
- availability of a signed and dated clinical trial contract between the sponsor and the Head of Trial Centre,
- approval/notification of the regulatory authority, e.g. competent authority,
- availability of the curriculum vitae of the principal investigator,
- availability of a signed and dated clinical trial protocol or immediately imminent signing of the clinical trial protocol,
- where applicable, availability of the proof of a medical licence for the principal investigator,
- for USA, availability of the Form 1572.

The investigator or delegate must maintain records of the product's delivery to the trial site, the inventory at the site, the use by each patient, and the return to the sponsor or alternative disposition of unused product(s).

These records will include dates, quantities, batch/serial numbers, expiry ('use by') dates, and the unique code numbers assigned to the investigational product(s) and trial patients. The investigator or delegate will maintain records that document adequately that the patients were provided the doses specified by the CTP and reconcile all investigational product(s) received from the sponsor. At the time of destruction at site or return (if applicable) to the sponsor and/or appointed CRO, the investigator or delegate must verify that all unused or partially used drug supplies have been returned by the clinical trial patient and that no remaining unused supplies are in the investigator's possession.

Proprietary confidential information.

© 2017 Boehringer Ingelheim International GmbH or one or more of its affiliated companies. All rights reserved.

This document may not - in full or in part - be passed on, reproduced, published or otherwise used without prior written permission.

4.1.9 Drug acceptability

Acceptability of the drug formulations in children per EMA/CHMP/QWP/805880/2012 Rev2 will be assessed using drug acceptability questionnaires for patients, parents/caregivers and investigator/site staff. Drug acceptability will be assessed after completion of the first course of treatment with the given formulation.

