Informed consent /patient assent	x ⁵											
Demographics	x											
Medical history	x											
Physical examination including neurological exam in patients with brain tumours	x	x	x	x	x	x	x	x	x	x		
Ophthalmologic examination	x									x		
Pulmonary examination ⁶	x	x					x		x	x		
Performance score ²²	x	x					x		x	x		
Vital signs	x	x	x	x	x	x	x	x	x	x		
Height ⁷	x								x ⁷			
Weight	x	x		x	x	x	x	x	x			
Safety laboratory tests ⁸⁻⁹	x	x ⁸		x ⁹	x ⁹	x ⁹	x	x ⁹	x	x ⁸		
Pregnancy test (if appl.) ¹⁰	x									x		
12 lead-ECG ¹¹	x			x					x ¹¹	x		
LVEF echo	x						x		x ¹²	x		
Disease assessment imaging ¹³	x								x ¹³	x		
Tumour marker(s) ¹⁴	x						x		x	x		
Tumour sample tissue availability ²³	x											
Review in-/ex- criteria	x											
Dose assessment	x						x ¹⁵	x ¹⁵	x ¹⁵			
Dispense trial drug ¹⁶		x					x		x			
Afatinib administration		Continuous oral once daily, fasted										
Pharmacokinetics		x ¹⁷	x ¹⁷	x ¹⁷	x ¹⁷							
Adverse events	x	x		x	x	x	x ¹⁸	x	x	x	x	x ¹⁹
Concomitant therapies	x	x		x	x	x	x	x	x	x	x	
Compliance check				x			x		x	x		
Patient diary check			x	x	x	x	x		x	x		
Eligibility for treatment continuation							x		x			
Conclusion of treatment										x		
Conclusion of patient participation											x	
Survival status												x

- All courses are of 4 weeks duration (28 days). Day 1 of a new course should take place on day 29. Patients may continue on treatment for unlimited courses until the criteria for stopping medication are met (see [Section 3.3.4](#)). Visits are performed weekly for the first course. At course 2, visits will take place every 2 weeks ([Visit 2 day 8](#) and visit 4 day 22 are no longer requested). From course 3 onwards, only visits “1” are required.
- EOT= end of treatment – When the decision is taken to permanently discontinue the study medication, the EOT visit must be performed within 7 days after last administration of afatinib. If the decision is taken at a scheduled visit, the EOT visit will be performed instead of the scheduled visit. Examinations performed at this time may need to be renamed for the actual visit conducted.
- FU= safety follow-up 28 to 30days after last afatinib administration. With the FU visit the patient will have completed his/her trial participation.
- OP= observation (post-trial) period. Collection of information on vital status every 3 months. Information could be collected from the patient’s notes or by telephone contact. A formal visit is not required.

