4.1.4 Drug assignment and administration of doses for each patient

Patients will be administered a single oral dose of afatinib each day. Treatment will be applied continuously until the development of progressive disease or unacceptable adverse events.

The medication should be taken at the same time each day (± 2 hours) without food (at least one hour before or at least three hours after a meal). If above time intervals cannot be adhered to in patients ≥ 1 year and < 2 years, time and type of food consumed within the critical application window for afatinib has to be recorded in the patient diary.

Missed doses of afatinib can be made up during the same day as soon as the patient remembers. However, if the next scheduled dose is due within 8 hours then the dose must be skipped and patients should take the next scheduled dose at the usual time. Patients with emesis must not take a replacement dose.

Proprietary confidential information.

© 2017 Boehringer Ingelheim International GmbH or one or more of its affiliated companies. All rights reserved.

This document may not - in full or in part - be passed on, reproduced, published or otherwise used without prior written permission.

Depending on age, BSA (see [Appendix 10.7](#)), dose strength and individual preference, afatinib film-coated tablets or liquid formulation prepared from afatinib capsules and solvent for oral solution may be applied.

Assuming comparable exposure for both formulations (see [Section 1.2](#)), the oral solution and the film-coated tablets may be used interchangeably when determining the MTD, in case of matching doses (deviation $\pm 10\%$) as specified in [Table 4.1.4.1](#). However, individual patients shall not switch between formulations as long as this is not necessitated by dose adaptations due to changing weight or BSA, or changes in the clinical health status or if patient adherence to treatment is otherwise endangered. **In any case, it must be attempted to keep all patients on their starting formulation for their first treatment cycle. This will be crucial for MTD determination.**

BSA has been recommended as the principal basis for drug dosage in the majority of chemotherapy regimens in adults and children ([R13-1191](#); [R13-1141](#); [P13-03365](#)).

For the current afatinib development in paediatric patients, allometric scaling was used to support estimation of a starting dose for different age groups based on the approved adult dose (40 mg).

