Visit 1 (day 1)

This visit should take place at day 29 from start of treatment and should serve for confirming patient's eligibility for treatment continuation

- Depending on the patient status, the investigator has to perform a disease assessment on patient's eligibility for the next treatment course. This might include but is not limited to:
 - Imaging findings (requested only every 2 courses: course 3 visit1, C5V1, C7V1...)
 - Tumour markers in blood or urine if indicated
 - Bone marrow if indicated

In case treatment discontinuation is required at this visit, please complete the EOT visit instead of this visit.

For patients included in the dose escalation part, a DLTs evaluation should be provided before to start a new course of treatment.

C2V1 visit should include:

Patient acceptability	Completion of acceptability questionnaires by patients, parents/caregiver and investigator/site staff Special note: at any time, if the patient switches from his/her initial formulation to the other, the questionnaires should be completed again after 28 days of intake of the new formulation.
Quality of life questionnaire	For MTD expansion cohorts/Phase II part only
Repeated procedures	Physical examination and vital signs; weight; blood sampling for safety lab; update on concomitant therapies and adverse events
Performance score	Lansky for patients ≤ 12 years or Karnofsky for patients older than 12 years at time of informed consent
Cardiac assessment	LVEF echocardiography shall be performed and the results must be documented in source data and eCRF for DLT evaluation
Patient diary	Check for completion
Compliance check	Check on trial drug compliance
Eligibility for treatment continuation	Confirm eligibility for further treatment
If the patient eligibility for further treatment is confirmed:	
Dose assessment	Assess appropriateness of the afatinib dose
Dispense trial drug	New afatinib kit(s) must be dispensed to the patient/parent(s)/legal guardian

Proprietary confidential information.

© 2017 Boehringer Ingelheim International GmbH or one or more of its affiliated companies. All rights reserved.

This document may not - in full or in part - be passed on, reproduced, published or otherwise used without prior written permission.

	(recalculate BSA for allocation of dose) for a daily drug intake along this treatment course
--	--

Visit 2 (day 15)

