6.2.3 End of treatment and follow-up period

End Of Treatment visit

This visit will take place as soon as a decision is made to permanently discontinue trial treatment.

The EOT visit will include the following actions:

Repeated procedures	Physical examination and vital signs; blood sampling for safety lab; update on concomitant therapies and adverse events
---------------------	---

Proprietary confidential information.

© 2017 Boehringer Ingelheim International GmbH or one or more of its affiliated companies. All rights reserved.

This document may not - in full or in part - be passed on, reproduced, published or otherwise used without prior written permission.

Ophthalmological examination	To exclude keratitis
Pulmonary examination	To exclude ILD
Pregnancy test	To be performed in post-menarchal female patients who are of childbearing potential
Performance score	Lansky for patients \leq 12 years or Karnofsky for patients older than 12 years at time of informed consent
Cardiac assessment	
 • LVEF echocardiography • 12 lead-ECG as detailed in Section 5.2.4
Assessment of the tumour disease	Depending on the tumour type, an assessment of the tumour disease has to be reported in the eCRF based on: 
 ○ imaging findings ○ tumour markers in blood or urine if indicated ○ clinical findings ○ bone marrow if indicated
Patient diary	Check for completion
Compliance check	Check on trial drug compliance
Conclusion of treatment	To confirm permanent treatment discontinuation

Follow-up visit for safety (28-30 days after last afatinib intake)

Safety update	Update on concomitant therapies and adverse events
Conclusion of patient participation	Confirmation of trial discontinuation for the patient

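### Acceptability is rated only after 28 days on a formulation, so children who leave it earlier go unrated and acceptability may be overstated

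*Protocol*

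**What the plan says.** Protocol Section 4.1.9 commits to assessing the acceptability of the formulations in children by questionnaire, and sets the time: "Drug acceptability will be assessed after completion of the first course of treatment with the given formulation". The flow chart's first footnote gives a course length of 28 days.

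Section 6.2.2 puts this into practice at C2V1: "This visit should take place at day 29 from start of treatment". The first item listed there is "Completion of acceptability questionnaires by patients, parents/caregiver and investigator/site staff". If a child changes formulation at any time, "the questionnaires should be completed again after 28 days of intake of the new formulation".

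Three other provisions decide who reaches that point:

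- Stopping at day 29 (Section 6.2.2): "In case treatment discontinuation is required at this visit, please complete the EOT visit instead of this visit".
- The EOT list (Section 6.2.3), opened by "The EOT visit will include the following actions", covers examinations, laboratory tests, tumour assessment, diary and compliance. It shows no acceptability questionnaire.
- Switching (Section 4.1.4) is discouraged, but allowed for dose adaptation, for a change in clinical status, "or if patient adherence to treatment is otherwise endangered".

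Section 4.1 also foresees older children who do not accept the tablets and offers them the oral solution.

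**The concern.** Acceptability is an outcome that can cause its own missing data. A child who refuses a formulation, or cannot take it, is among those most likely to leave it early, and the rating is requested only from those who stayed 28 days. Section 4.1.4 recognises this route by allowing a switch when adherence is at risk.

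At stake is whether the trial can say how acceptable the tablets and the oral solution are to all children who started them, or only to those who managed a full course. An opinion not collected when the child leaves the formulation cannot be recovered at analysis. Acceptability is not among the primary or secondary endpoints in Protocol Section 5, so the trial's main conclusions are not affected.

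**Working it through.** **Step 1. Who is rated.** Following each route through Protocol Sections 4.1.9, 6.2.2 and 6.2.3:

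| Child's course | Visit that follows | Rating of the formulation left |
|---|---|---|
| Stops before day 29 | EOT | None listed |
| Stops at the day-29 visit | EOT in place of C2V1 | None listed, although the course may be complete and 4.1.9 would then call for one |
| Switches before day 29 and continues | C2V1, then a repeat after 28 days on the new formulation | None asked at the switch; the text does not say which formulation the C2V1 answer rates |
| Stops or switches after C2V1 | Later visits | Already rated at C2V1 |
| Switches, then leaves the second formulation within 28 days | EOT or a later visit | None required for the second formulation |

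The gap is confined to children who leave a formulation before, or at the visit that follows, 28 days on it.

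**Step 2. Effect on the estimate.** The documents state no acceptability figure, so there is none to reproduce. Let A be the true acceptable share among all children who started a formulation, m the share of non-accepters who leave unrated, and e the share of accepters who leave unrated for other reasons such as progression or toxicity. Then

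observed = A(1−e) / [A(1−e) + (1−A)(1−m)].

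A, m and e are all assumptions; the documents supply none of them.

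**Step 3. Illustrations with A = 80%.**

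- m = 25%, e = 0: 0.80 / (0.80 + 0.20 × 0.75) = 84.2%
- m = 50%, e = 0: 0.80 / (0.80 + 0.20 × 0.50) = 88.9%
- m = e = 20%: 0.64 / (0.64 + 0.16) = 80.0%, no bias
- m = 0, e = 20%: 0.64 / (0.64 + 0.20) = 76.2%, bias downward

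For A between 60% and 90% with e = 0, the overstatement is about 2 to 7 points at m = 25%, 5 to 15 points at m = 50%, and 10 to 40 points in the extreme case m = 100%.

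**Step 4. In patient numbers.** Take 38 children, the upper limit for the expansion part in Section 3.3, used here only for scale, and suppose 30 find the formulation acceptable: 30/38 = 78.9%. If one non-accepter is unrated, the result is 30/37 = 81.1%; if two, 30/36 = 83.3%; if four, 30/34 = 88.2%. At this sample size a few unrated refusals move the figure visibly.

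**The case against.** The other side has several sound points.

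- **Later leavers are rated.** A reader might infer that any child who stops or switches goes unrated. That is not so: anyone who leaves the first formulation after C2V1 has already rated it.
- **The C2V1 answer of an early switcher.** A reader might infer that it rates the new formulation. The text does not say this. C2V1 lists the questionnaires without condition, and a switch means completing them a further time later. The fair reading is ambiguity.
- **Few refusals may occur.** Inclusion criterion 11 requires children to be able and willing to take afatinib orally, and Section 4.1.4 asks that the starting formulation be kept through the first cycle. Both should reduce the numbers. Neither removes the route.
- **The youngest children.** A reader might infer that the oral solution in the youngest is hit hardest. For switching, the documents do not support this. Table 4.1.4:1 has no tablet below 1 m² at level 0, the established MTD, so these children have no tablet to switch to, and the non-acceptance that Section 4.1 names concerns tablets in older children. A small child who refuses the solution could still stop and go unrated, but no frequency is given.
- **Other records exist.** Reasons for withdrawal (Section 3.3.4.1), diaries and compliance checks (Section 4.3) give partial information. None of them is a rating of a formulation.
- **Some text is not visible.** Section 5.3.2 is blank and flow-chart footnotes 20 and 21 are absent, so a further rule cannot be excluded. These gaps are not counted against the plan.

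These points limit the scope and the certainty. They leave standing that the visible rule collects no clear rating of a formulation left early.

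**Conclusion.** The point holds as a modest design gap. In the visible text, acceptability is measured in children who complete 28 days on a formulation. The result may be overstated, because non-acceptance is one of the reasons for leaving early.

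The documents do not show that it will be overstated, or by how much. Upward bias requires non-accepters to leave unrated more often than accepters (m > e). It is zero when the two rates are equal and reverses when accepters are lost more often.

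A reader might be tempted to size the bias from Section 7.6, where 24 evaluable patients are needed and 30 were planned: 6/30 = 20%. That is an all-cause allowance for early drop-out or non-evaluability for DLT in the dose-finding part. It includes losses unrelated to the formulation. It can also include a child without a DLT who misses more than 25% of doses (Section 4.3; SAP Section 5.1), who may still reach C2V1 and give a rating. Even taking 20% unrated and 70% true acceptability, the answer depends on the share h of unrated children who are non-accepters, with observed = (0.70 − 0.20(1−h)) / 0.80. This gives 62.5% at h = 0, 70% at h = 0.3, 75% at h = 0.5 and 87.5% at h = 1. The allowance therefore fixes neither the direction nor the size.

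The change is worth making because it is cheap and the missing answers cannot be obtained later. It does not bear on the dose-finding or response conclusions.

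**What to change.** Amend Protocol Sections 4.1.9, 6.2.2 and 6.2.3:

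1. Keep the C2V1 questionnaire. In addition, complete the existing questionnaire at a switch, or at the EOT visit, if the formulation being left has not yet been rated.
2. Record on the form which formulation is being rated. This also resolves the C2V1 ambiguity for a child who switched in course 1.
3. Report by formulation the number of children who took at least one dose, the number rated, and the number unrated with reasons.
4. Add a sensitivity summary in which a stop or switch because of refusal or inability to take the formulation counts as not acceptable. This is a choice of estimand, so it should stand beside the observed ratings and not replace them.

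The cost is a short wording change and a few minutes with an existing form at a contact that already takes place. The downside is a possibly less favourable acceptability figure.

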4.2 CONCOMITANT THERAPY, RESTRICTIONS, AND RESCUE TREATMENT

4.2.1 Rescue medication, emergency procedures, and additional treatment(s)

Rescue medication

Rescue medications to reverse the actions of afatinib are not available. There is no specific antidote for overdosage with afatinib. Potential adverse events should be treated symptomatically. In cases of suspected overdose, afatinib should be withheld and supportive care initiated. If indicated, elimination of unabsorbed afatinib may be achieved by emesis or gastric lavage.

Common adverse events of afatinib treatment observed in adults with specified management recommendations and/or requirements include diarrhoea, mucositis and rash/acne. To improve tolerability and the probability of clinical benefit, patients should receive prompt and appropriate supportive care at the first signs of symptoms. Suggested treatments for AEs are described below.

Concomitant treatments

Concomitant medications or therapy to provide adequate supportive care may be given as clinically necessary.

After study enrolment, palliative radiotherapy may be given for bone pain or for other reasons (e.g. bronchial obstruction, skin lesions), provided that the total dose delivered is in a palliative range according to institutional standards. The irradiated area must not be used for tumour response assessment. During palliative radiotherapy, study treatment should be paused and be resumed once the patient has recovered from any radiation associated toxicity. If medication is interrupted for more than 14 days, the decision to continue will be made by the BI clinical monitor in agreement with the investigator. Continuous interruption of >28 days due to palliative radiotherapy will not be allowed.

All concomitant therapies, including anaesthetic agents (except pre-planned anaesthetic agents e.g. related to imaging exams), vitamins, homeopathic/herbal remedies, nutritional supplements, must be recorded in the eCRF during the screening and treatment period, starting from the date of signature of informed consent for trial participation, and ending at the EOT visit. After the EOT visit, only concomitant therapy indicated for treatment of an AE has to be reported.

In case of major surgery (as judged by the investigator), it is recommended to stop treatment with afatinib around one week prior to the surgery, and to restart treatment after complete

Proprietary confidential information.

© 2017 Boehringer Ingelheim International GmbH or one or more of its affiliated companies. All rights reserved.

This document may not - in full or in part - be passed on, reproduced, published or otherwise used without prior written permission.

wound healing. If afatinib is interrupted for more than 14 days, the decision to continue will be made by the BI Clinical Monitor in agreement with the investigator.

Emergency procedures

Careful assessment of all patients with an acute onset and/or unexplained worsening of pulmonary symptoms (dyspnoea, cough, fever and demand for oxygen supplementation) should be performed to exclude interstitial lung disease (ILD). Study drug should be interrupted pending investigation of these symptoms. If interstitial lung disease is diagnosed, study drug must be permanently discontinued and appropriate treatment instituted as necessary.

Patients who present with symptoms of keratitis, such as acute or worsening eye inflammation, lacrimation, light sensitivity, blurred vision, eye pain and/or red eye should be referred promptly to an ophthalmic specialist. If a diagnosis of ulcerative keratitis is confirmed, treatment with afatinib should be interrupted or discontinued. If keratitis is diagnosed, the benefits and risks of continuing treatment with afatinib should be carefully considered. Afatinib should be used with caution in patients with a history of keratitis, ulcerative keratitis or severe dry eye. Contact lens use is a risk factor for keratitis and ulceration.

In case the patient develops acute onset of symptoms indicative of cardiac failure and/or CTCAE Grade ≥ 2 LVEF decrease and/or $\geq 20\%$ decrease of LVEF from baseline, study drug should be interrupted pending investigation of symptoms. The patient should be monitored closely for recovery. If patient has not recovered despite appropriate treatment to Grade ≤ 1 or baseline within 14 days study treatment must be permanently discontinued.

